Audio/visual Zoom recording will begin as soon as the moderator begins the Zoom session. The resulting mp4 recordings will be temporarily stored on a secure, encrypted, password-protected Rutgers server and uploaded to a transcription company, ADA Transcription, via a secure web portal. The transcripts will be returned to the research team through the same portal. The mp4 files will be destroyed after a research team member has checked the transcripts for accuracy. Only the research team and the transcription company will have access to the audio files and transcripts.

Aim 2 procedures include a one-time baseline survey followed by saliva testing. After enrollment and completion of online questionnaires, saliva test kits are ordered and mailed to the participant by Vault Health, Inc., a fee for service vendor that is not engaged in research, with a prepaid envelope to return the sample. Vault Health remotely supervises participants while they collect their saliva sample (via Zoom video call if needed) and reports results to participants. Participant's role in the study ends in phase 1 at the completion of the virtual community conversation/focus group/key informant interview and for phase 2 after receipt of their test result.

B. Data Points

N/A—No long term follow-up is planned.

C. Study Duration

The proposed project will be conducted over a 2-year period (See Section 1.10 for timeline). Aim 1 will be completed by Month 6. Aim 2 will be completed by Month 18. Final data analyses, preparation of manuscripts, and final dissemination materials will be completed by Month 24.

D. Endpoints

N/A

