1.6 Study Variables

In Aim 1, we will co-design, develop and implement an innovative, HCW-centric outreach intervention strategy to engage Black and Latinx minority communities. We will explore community perceptions about COVID-19 testing, treatment, and vaccination to design COVID-19 testing materials and messages that are culturally tailored to address concerns of Black and Latinx minority communities. In Aim 2, we will conduct a mixed methods study to evaluate the effectiveness and cost of: (1) the HCW-focused outreach intervention strategy versus (2) standard community engaged outreach, working with community based organizations (CBOs). We will explore contextual factors (individual, family, and community) affecting COVID-19 testing implementation outcomes and scalability. The primary outcome will be uptake of COVID-19 testing in the targeted populations.

A. Independent Variables, Interventions, or Predictor Variables

RADxUP has provided a list of common data elements that include PhenX Toolkit items with Spanish translations that will be collected across funded consortia projects. Data elements include demographics, medical history, health status, vaccine acceptance, COVID-19 testing experience and trusted information sources. We will also assess trust in healthcare using the Revised Healthcare System Distrust Scale; 9 items.

B. Dependent Variables or Outcome Measures

Our primary outcome, testing, will be measured through Vault's receipt of a saliva kit from the participant with virus test results provided directly to participants as well as to the study team.

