1.9 Data Collection

A. Primary Data Collection

Aim 1:

The main data source will be audio/video recordings of the virtual focus groups and community conversations. Supplemental key informant interviews that use the approved focus group guide questions and script will be conducted with HCW. Digital recordings of conversations will be transcribed verbatim and imported into ATLAS.ti™ to facilitate coding and analysis.

Aim 2: There are four main sources of materials:

1. **COVID-19 testing data derived from saliva samples provided at home by participants** (See section 1.8). Saliva will be collected from participants ages 4 and above.
2. **Questionnaire data provided by participants through REDCap:** Questionnaire data will be completed by participants aged 18 and older. Parents or legal guardians will be responsible for completing questionnaires for children ages 4 to 17. Questionnaires will include items regarding demographics, possible COVID-19 exposures and testing history, overall health and lifestyle. Additional REDCap questionnaires related to acceptance of testing will query health literacy, English language proficiency, patient activation, attentional style, and patient trust. Survey data will be automatically downloaded from REDCap for direct import into a statistical analysis software program, e.g., SAS.
3. **Focus group data from virtual community conversations and community engagement virtual salons:** Focus groups of virtual community conversations and community engagement virtual salons as well as key informant interviews will be conducted via Zoom.
4. **Key informant data provided by select HCW ambassadors, community and healthcare organization stakeholders regarding implementation of the outreach strategies.** Field notes, meeting minutes and an activity tracker from administrative meetings with members of the participating organizations will be collected.

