4.3 Number of Subjects

A. Total Number of Subjects

We anticipate a total of 3000 participants will be enrolled across the two study aims.

Aim 1: We recruited 13 groups and 8 individual interviews with stakeholders who identified as Black and/or Latinx (n=111 individuals).

Aim 2: The goal is to enroll approximately 1000 participants in each of the two study arms (N=2000) over a 12 month period.

We are experiencing a high loss to follow-up rate in Aim 2. Though interest, consent rates and survey completion are high there is also a high rate of loss to follow-up. COVID-19 testing is the study outcome and uptake among participants is low. Therefore, we may need to enroll more than 1000 per arm.

B. Total Number of Subjects If Multicenter Study

N/A

C. Feasibility

For Aim 1 and Aim 2 community based organization arm, drawing from long-established relationships and community partners of MPIs [name], [name], and [name] we have engaged 18 community organizations in the design and development of this project. Organizations serve the cities of Newark, Elizabeth, Irvington, Hillside, Caldwell, Paterson, New Brunswick, Perth Amboy, and their surrounding areas. They range in size, scope and focus from faith-based organizations to large social service groups.

For the Aim 2 HCW arm, our current COVID-19 surveillance cohorts include nearly 4000 HCWs, of whom we estimate 32% (n~1300) meet criteria to serve as ambassadors. We anticipate that approximately 1000 more HCWs from Parker Health and the Visiting Nurse Association will be eligible.

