Quantitative: To compare participation rates in the two arms, our primary outcome, we will use data on the number of tests performed per month (over the up to 12 month study period). For each intervention, the start time is the date of first attempted contact with potential participants and the end date is either the end of the study period, or the date at which the 1000th individual was tested (whichever comes first). We assume that the number tested follows a Poisson distribution within the time period. We will test the null hypothesis that there is no difference between the two interventions, and also report a 95% confidence interval for the rate ratio. Secondly, we will examine the proportion of tested participants from vulnerable and underserved populations of interest (e.g. Black and Latinx, immigrants, children, and low-income households) in each arm through logistic regression models. We will additionally examine proportion of positive tests in the two study arms to examine whether recruitment through index HCWs taps into more highly exposed participant groups, as hypothesized. To do so we will fit logistic regression models, where the outcome is positive test results (yes/no) and the primary predictor is study arm, adjusting for covariates including participant age, race/ethnicity, sex, occupation, and highest level of educational attainment. Power calculations for this aim are based on the primary outcome measure, testing uptake rate. We report power for rate ratios (RR; ratio of rate in comparison arm relative to intervention arm) of 1.15, 1.2, and 1.3, when expected tests per month in the intervention arm range from 80 to 120 (Table X). We will have about 80% power or greater for RR of 1.15 or greater. To test hypothesis 2B, we will compare participants in the two arms on key characteristics that may be barriers to testing (participant trust, health literacy, English proficiency, and patient activation). We will do so through linear regression models, adjusting for covariates including participant age, race/ethnicity, sex, and highest level of educational attainment.

RR	80	100	120
1.15	0.78	0.82	0.81
1.2	0.94	0.96	0.95
1.3	0.99	0.99	0.99

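### The positivity comparison covers only people with a test result but is read as showing whom the HCW route recruits; if test completion depends on exposure differently by arm, the odds ratio can mislead

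*Combined protocol and SAP*

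**What the plan says.** Section 6.1 (Aim 2, Quantitative) describes a logistic model in which "the outcome is positive test results (yes/no) and the primary predictor is study arm". It is to be fitted "adjusting for covariates including participant age, race/ethnicity, sex, occupation, and highest level of educational attainment". Its purpose is to "examine proportion of positive tests in the two study arms to examine whether recruitment through index HCWs taps into more highly exposed participant groups, as" the plan expects.

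Section 1.6 B says that testing "will be measured through Vault's receipt of a saliva kit from the participant", so a participant whose kit never arrives has no value for the outcome.

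On how many reach that point, section 4.3 A reports: "Though interest, consent rates and survey completion are high there is also a high rate of loss to follow-up". It adds that test uptake is low, and its only response is that each arm may need more than 1000 enrollees. It gives no uptake figure, overall or by arm.

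The survey comes before the kit. Section 1.3 A: "After enrollment and completion of online questionnaires, saliva test kits are ordered and mailed to the participant by Vault Health, Inc". Section 1.9 A: "Questionnaires will include items regarding demographics, possible COVID-19 exposures and testing history, overall health and lifestyle". Section 4.4 C adds a step between the two: at the end of the survey the participant must agree to give saliva and enter a mailing address.

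No section describes, for this model, any handling of enrollees without a result, a comparison of tested with untested people, or a sensitivity analysis.

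**The concern.** The question is about the people the HCW route brings into the study, but the data come from the subset who completed a test. Section 4.3 suggests that this subset is much smaller than the enrolled group. The arm odds ratio therefore mixes two things: who was recruited, and who among them went on to test.

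The documents make it plausible that the second part differs by arm, without showing that it does. Section 4.1 B treats the consequences of a positive result for work and basic needs as a barrier, and describes resource lists to offset it under the HCW arm. The account of the comparison arm does not mention these lists, although that arm may share other Aim 1 materials. Some HCW ambassadors also come from two cohorts that had already been tested for SARS-CoV-2 (section 1.4). No such earlier testing is described for the community arm.

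At stake is a statement that the HCW route reaches more, or less, exposed groups when the recruited groups may be alike. More enrolment would not help: it narrows the interval around the same biased value.

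**Working it through.** **Inputs.** From the documents: the outcome, predictor and covariates (6.1); a result requires a received kit (1.6 B); loss is high and uptake low, with no figures (4.3); the target is about 1000 per arm (4.3). Not in the documents: expected positivity, the share exposed, and return probabilities by exposure or arm. These are assumed below and only show what is possible. The plan states no power or expected positivity for this comparison. The power table in 1.5 and 6.1 concerns tests per month and does not bear on it.

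**Step 1: what selection does to the odds ratio.** In one arm, let r_I and r_U be the probabilities of having a result among infected and uninfected enrollees. The odds of a positive among the tested equal the odds among the enrolled times r_I/r_U. Hence

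tested-only OR = true OR × (r_I/r_U in the HCW arm) ÷ (r_I/r_U in the community arm).

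The bias vanishes if the ratio is the same in both arms, whatever the total uptake.

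**Step 2: identical recruited groups, equal total uptake.** Assume 20% exposed in both arms, with infection in 20% of the exposed and 2% of the unexposed. True positivity is 0.2×0.20 + 0.8×0.02 = 0.056 in each arm, so the true OR is 1. With return probabilities a (exposed) and b (unexposed):

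positivity among tested = (0.2·a·0.20 + 0.8·b·0.02) ÷ (0.2·a + 0.8·b).

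The community arm returns 40%/40%: (0.0160 + 0.0064)/0.40 = 5.6%.

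| HCW-arm return, exposed/unexposed | Uptake | Positivity among tested | OR against 5.6% |
|---|---|---|---|
| 80% / 30% | 0.16 + 0.24 = 0.40 | (0.0320 + 0.0048)/0.40 = 9.2% | 1.71 |
| 60% / 35% | 0.12 + 0.28 = 0.40 | (0.0240 + 0.0056)/0.40 = 7.4% | 1.35 |
| 30% / 42.5% | 0.06 + 0.34 = 0.40 | (0.0120 + 0.0068)/0.40 = 4.7% | 0.83 |

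For the first row: (0.092/0.908) ÷ (0.056/0.944) = 1.71. These are crude odds ratios. The planned covariates would remove only the part of the selection that they carry.

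**Step 3: unequal total dropout alone.** Keep the HCW arm at 80%/30% and halve both probabilities in the community arm, to 40%/15%. Community positivity is (0.0160 + 0.0024)/0.20 = 9.2%. Uptake is 40% against 20%, yet positivity is 9.2% in both arms and the OR is 1.00.

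**Step 4: how often this would look significant.** Assume true positivity of 5% in both arms, return unrelated to infection in the community arm, and a two-sided 5% test of two proportions.

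| r_I/r_U in HCW arm (= false OR) | Tested-only positivity | 1000 tested per arm | 300 tested per arm |
|---|---|---|---|
| 1.25 | 6.2% vs 5.0% | 21% | 9% |
| 1.5 | 7.3% vs 5.0% | 58% | 22% |
| 2 | 9.5% vs 5.0% | 97% | 57% |

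At a ratio of 1.5 and 1000 tested per arm, moving true positivity from 2% to 10% moves the chance from 29% to 84%.

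**Step 5: can baseline data repair it?** In the first row of step 2, weight each tested person by 1/P(result | arm, exposure). Positives become 0.0320/0.8 + 0.0048/0.3 = 0.040 + 0.016 = 0.056. The total becomes 0.16/0.8 + 0.24/0.3 = 1. Positivity returns to 5.6% and the OR to 1.00. This holds only if, within arm, completing a test depends on nothing related to infection beyond the recorded exposure.

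**The case against.** - **The target may be tested people.** Section 6.1 measures participation by counting tests, and the analysis just before this one concerns tested participants. On that reading the tested-only figure is a valid description. This stands in part. The sentence nevertheless draws its conclusion about recruitment, so the wording has to settle which is meant.
- **The bias is not demonstrated.** A reader might infer that high loss to follow-up, or a difference in total loss between arms, already makes the comparison wrong. It does not (step 3). No document shows that test completion depends on exposure, or does so differently by arm. This stands.
- **Exposure is missing from the covariates.** A reader might take this as the defect. It is not: exposure is the difference being sought, and adjusting for it would remove that difference. The covariate list is also open-ended.
- **Baseline data are incomplete.** Survey completion is described as high, not full, so exposure is known for survey completers rather than for every enrollee. Loss can also occur at the saliva agreement and address step, before any kit is mailed. Both points stand.
- **The remedies have limits.** The documents give neither the wording nor the recall window of the exposure items, and HCWs may report exposure differently. Weights cannot capture symptoms or contacts arising after the survey, and may be unstable if uptake is very low. This stands, and is why neither should replace the laboratory result.
- **The analysis is minor.** It is additional, has no stated power, and is neither Hypothesis 2A nor 2B as listed in section 1.1. This stands.

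**Conclusion.** The concern holds as a gap between the conclusion planned and the people analysed. Under the assumed inputs, identical recruited groups can yield tested-only odds ratios from 0.83 to 1.71, so the direction is not predictable. A one-arm return ratio of 1.5 at 5% true positivity would give a false significant difference 58% of the time with 1000 tested per arm, and 22% with 300.

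The condition is that the infected-to-uninfected ratio of test completion differs by arm in a way the planned covariates do not absorb. A reader might go further and infer that the positivity result will be biased, or that the primary comparison is compromised. The documents support neither: they give no uptake by arm and no link between exposure and return, and the primary outcome counts tests without using their results. The point merits a change before analysis, at a severity suited to an additional analysis.

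**What to change.** In section 6.1:

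1. Keep the planned tested-only logistic model, but word its conclusion as applying among those tested.
2. As supporting evidence, compare baseline reported exposures and testing history between arms in all survey completers. Within each arm, compare tested with untested completers on the same items.
3. Add a sensitivity analysis that weights each tested participant by the inverse of the arm-specific probability of having a test result. Model that probability among survey completers from baseline exposure, testing history, health status and demographics. Cover both loss at the saliva agreement and address step and non-return of kits, and truncate extreme weights by a rule set in advance. Report it beside the unweighted result.
4. Do not add exposure as a covariate in the outcome model.

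The cost is SAP wording, descriptive comparisons and one weighting model; the survey already collects these variables before a kit is mailed. The drawbacks are wider intervals when uptake is low, correction only for reasons measured at baseline, and self-reported exposure that HCWs may report differently.

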The RWJSS involves 3904 hospital employees and affiliated clinicians who received SARS-CoV-2 virus and antibody testing at a single time-point and are being followed for self-reported COVID-19 prospectively. 1202 (30.8%) tested participants are URM. A total of 9.8% of participants tested positive for SARS-CoV-2 virus or antibodies, with higher rates observed among Black (14.8%) and Latinx (15.5%) HCW. Notably, compared to non-Hispanic White participants, the odds of a positive test were twofold higher among Black (OR: 2.15, 95% CI: 1.55, 2.97) and Latinx participants (OR: 1.94, 95% CI: 1.42, 2.66). Importantly, infection rates were especially high among lower status medical roles (e.g., technicians, phlebotomists) as well as hospital support roles (dining/food, maintenance /housekeeping, security/support) (Figure 7).

Figure 7. Prevalence of SARS-CoV-2 infection based on role in the hospital and direct patient care responsibilities

Notes: ED, emergency department; EMT, emergency medical technician; NP, nurse practitioner; OR, operating room; PA, physician's assistant; PT, physical therapist; OT, occupational therapist; RT, respiratory therapist; ST, speech therapist

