Finally, an additional potential risk may be receipt of an inaccurate test result. Our saliva test was the first saliva-based test to detect SARS-CoV-2 that was granted emergency use authorization by the FDA, and it is the only one authorized for at-home self-collection in the U.S. To date, 200,000 tests have been performed. The test is very sensitive for the presence of SARS-CoV-2, with 98% of tests providing either a positive or a negative result, and only 2% of tests providing an inconclusive result. The test can detect fewer than 10 copies of viral genes per milliliter of saliva, and it can detect the presence of virus in the saliva within 2 days of infection and up to 28 days after infection. Across all known gene sequences of SARS-CoV-2, the test detects the ones in the genes of interest ~100% of the time, making it highly sensitive and specific for those genes. While false positive and false negative rates for this test cannot be calculated currently (the lab does not receive data on what happens to patients after they receive the test), emerging data about false negative rates of saliva-based COVID tests are showing that the false negative rate may be closer to 10%, which is significantly lower than those of nasopharyngeal swab-based tests, which are in the 25-35% range.

B. Procedures which Risk Harm to Embryo, Fetus, and/or Pregnant Subjects

N/A

C. Risks of Harm to Non-Subjects

N/A

D. Assessment of Social Behavior Considerations

N/A

E. Minimizing Risks of Harm

The investigative team will abide by the protocols laid out by our ongoing IRB-approved cohort surveillance studies. All data used for analysis will not contain any PHI. Data will be transferred according to safe data transfer policies utilized by both studies and stored on password protected, encrypted computers. All co-investigators will also sign a confidentiality agreement to prevent both a breach of confidentiality and deductive identification of the de-identified data. All study personnel have been trained in methods of maintaining confidentiality and have passed the Rutgers educational program requirement on the protection of human subjects (CITI training), Good Clinical Practice, and HIPAA regulations at regular intervals. In addition, audit trails, reports for monitoring and other checks will be made to ensure data integrity. These checks will be overseen by the study PIs and research team.

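### Arm positivity from a single virus test is read as exposure without a sampling-date term, so the contrast is confounded by the epidemic's course if the arms test in different calendar periods

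*Combined protocol and SAP*

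**What the plan says.** Section 6.1 plans, in addition to the primary rate comparison, to compare the "proportion of positive tests in the two study arms to examine whether recruitment through index HCWs taps into more highly exposed participant groups". The model is logistic: "the outcome is positive test results (yes/no) and the primary predictor is study arm". Its adjustment set is given in these words: "adjusting for covariates including participant age, race/ethnicity, sex, occupation, and highest level of educational attainment". Date of sampling is not named, although the word introducing the list leaves it open.

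Section 1.3 describes one test per participant: "Aim 2 procedures include a one-time baseline survey followed by saliva testing". On the assay, section 4.7 says that "it can detect the presence of virus in the saliva within 2 days of infection and up to 28 days after infection".

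The arms do not share a clock. Section 6.1 states: "For each intervention, the start time is the date of first attempted contact with potential participants". Each arm then stops at the end of the study period or at its 1000th test, whichever is earlier. Sections 1.9, 4.4 and 6.3 say that dates are randomly shifted when data are de-identified; they do not give the size or unit of the shift.

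The questionnaire in section 1.9 covers "possible COVID-19 exposures and testing history", but the positivity analysis does not use these items.

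**The concern.** Two things stand between a positive result and the conclusion that an arm reached more exposed people.

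The first is what the test measures. A single virus test with a window of about 28 days shows recent infection, not accumulated exposure. The team's own earlier hospital cohort used a broader measure (section 1.4: "A total of 9.8% of participants tested positive for SARS-CoV-2 virus or antibodies"), which also picks up past infection.

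The second is when the test is taken. The chance of a positive result depends on prevalence at that date. If one arm has more of its tests in a low-prevalence period, its positivity is lower whoever was recruited. None of the named covariates removes this.

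At stake is one stated conclusion, that recruitment through HCWs reaches more highly exposed groups. It could be missed or wrongly supported. The date shifting makes this a matter to settle in advance: if true month is not kept, the adjustment may not be possible later from the analysis file.

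**Working it through.** The documents give no expected positivity, effect size or power for this analysis, so there is no planned figure to reproduce.

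**Inputs from the documents.** 80, 100 or 120 tests per month in the HCW arm and rate ratios of 1.15, 1.2 and 1.3 (sections 1.5 and 6.1); a stop at 1000 tests or 12 months (section 6.1).

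**Assumptions.** Both arms start together and accrue at a constant rate. The HCW arm is the faster one, as Hypothesis 2A expects, so comparison rate = HCW rate / ratio. (The protocol words the ratio as comparison over intervention.) Prevalence among testers is 1% in the first six months and 3% afterwards, the same in both arms.

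**Step 1: timing.** Duration T = min(12, 1000/rate). Share of tests in the first six months = 6/T.

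**Step 2: spurious OR.** Arm positivity = share × 1% + (1 − share) × 3%. OR = odds(HCW) / odds(comparison).

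| HCW rate, ratio | T, HCW v comparison (months) | First-six-month share | Positivity | OR | OR if 3% then 1% |
|---|---|---|---|---|---|
| 80, any | 12 v 12 | 50% v 50% | 2.00% v 2.00% | 1.00 | 1.00 |
| 100, 1.15 | 10.0 v 11.5 | 60% v 52% | 1.80% v 1.96% | 0.92 | 1.08 |
| 100, 1.2 or 1.3 | 10.0 v 12 | 60% v 50% | 1.80% v 2.00% | 0.90 | 1.10 |
| 120, 1.15 | 8.3 v 9.6 | 72% v 63% | 1.56% v 1.75% | 0.89 | 1.08 |
| 120, 1.2 | 8.3 v 10.0 | 72% v 60% | 1.56% v 1.80% | 0.86 | 1.11 |
| 120, 1.3 | 8.3 v 10.8 | 72% v 55% | 1.56% v 1.89% | 0.82 | 1.16 |

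Last row in full: 0.72 × 1% + 0.28 × 3% = 1.56%; 0.554 × 1% + 0.446 × 3% = 1.89%; (0.0156/0.9844) / (0.0189/0.9811) = 0.82.

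**Step 3: can a true difference be reversed?** In the last row, (10.83 − 8.33)/10.83 = 23% of comparison tests fall after the HCW arm closes. Suppose that this tail alone falls in a high period and the true OR is 1.5 in favour of the HCW arm. The unadjusted OR is then:

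- 1.29 with positivity of 3% rising to 5% (attenuated, not reversed);
- 0.77 with 1% rising to 5%;
- 0.48 with 1% rising to 10%.

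Treating the true effect as a ratio R and the tail share as s, reversal needs a high/low prevalence ratio above 1 + (R − 1)/s. For R = 1.5 and s = 0.23 this is about 3.2; for s = 0.13 (100 per month, ratio 1.15) it is about 4.8.

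**Step 4: does a period term work?** This was simulated with 1000 per arm, a true OR of 1.5, positivity of 1% and 5%, and 20% (HCW) v 60% (comparison) of tests in the high period. That split is more extreme than the plan's rates give with a common start. Without a period term the median OR was 0.76, in the wrong direction in 85% of runs. With the term it was 1.50, wrong in 8%. With a 50% v 50% split the two models agreed (medians 1.47 and 1.48).

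**The case against.** The strongest reply is that the plan gives little reason to expect unequal timing. A reader might infer that a faster HCW arm necessarily samples in different months, so that success on Hypothesis 2A by itself distorts this contrast. The documents do not support that. Under the constant-rate Poisson assumption of section 6.1, a higher rate gives more tests in every month; it does not move them. Timing diverges only through an early stop at 1000 tests, staggered starts or uneven accrual. Section 1.10 schedules both arms in one row, and section 4.3 reports low testing uptake, which makes an early stop less likely. All of this stands, and it is why the lower end of the range is no bias at all.

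A second reply is that the distortion is small against sampling error. At 1000 per arm, 15.6 v 18.9 expected positives give an OR of 0.82 with a 95% interval of about 0.42 to 1.62 (standard error of the log OR 0.345). This is also fair, but random error does not excuse a systematic one that can be removed cheaply.

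Third, the covariate list is open-ended, so month is not excluded. True, but an unnamed term is not prespecified, and random date shifting may remove the means of adding it.

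Two further inferences should be resisted. The window covers 28/365, about 8%, of a year's infections at constant incidence, but it is the same in both arms, so that figure is not a measure of bias. And the higher infection rates in Black and Latinx staff in section 1.4 (14.8% and 15.5%) do not predict a difference between arms, because eligibility in both arms requires Black or Latinx self-identification.

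**Conclusion.** The point holds in conditional form. The planned contrast measures current or recent infection, and nothing named in the model protects it from differences in sampling date. The bias needs both unequal timing between arms and changing prevalence; with equal timing it is close to nil.

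On the plan's own rates, with a common start, a faster HCW arm and assumed prevalence of 1% and 3%, the spurious OR lies between 1.00 and 0.82, or between 1.00 and 1.16 with the order reversed. A reader might infer that the contrast will point the wrong way. That would need more: an early stop followed by a several-fold rise in prevalence, or staggered starts or uneven accrual, which section 6.1 permits but does not plan. The prevalence figures are assumptions, since the documents give none.

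This concerns an additional analysis. The primary uptake comparison is not touched by it.

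**What to change.** In section 6.1:

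- Add calendar month of sample collection to the positivity model, or coarser periods if positives are few.
- State that true collection month is kept in the analysis file, as an exception to the random date shifting in sections 1.9, 4.4 and 6.3.
- Describe the result as yield of current or recent infection.
- Compare the arms on COVID-19 exposures reported in the baseline questionnaire, as supporting evidence on the exposure question.

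Do not adjust for a self-reported previous positive test, or use it as the main exposure measure. HCW index participants come partly from the two cohorts that the team had already tested (sections 1.4 and 4.1), so the item would differ between arms through access to testing alone. It is also a marker of the exposure being compared, and section 1.9 mentions only testing history, which does not confirm that earlier results are recorded.

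The cost is a few sentences of plan text, one retained variable, one more comparison on data already collected, and some loss of precision from the period terms.
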